### Trademark Information

Trademarks of the GlaxoSmithKline group of companies
NONE

Trademarks not owned by the GlaxoSmithKline group of companies
ACTEMRA
Hypak
QuantiFERON
RIBA
SCF
SmartJect (Autoinjector)
UltraSafe Passive

## **12.2. Appendix 2: Modified List of Highly Effective Methods for Avoiding Pregnancy in Females of Reproductive Potential (FRP) and Collection of Pregnancy Information**

### **12.2.1. Modified List of Highly Effective Methods for Avoiding Pregnancy in Females of Reproductive Potential (FRP)**

This list does not apply to FRP with same sex partners, when this is their preferred and usual lifestyle or for subjects who are and will continue to be abstinent from penile-vaginal intercourse on a long term and persistent basis.

- Contraceptive subdermal implant
- Intrauterine device or intrauterine system
- Oral Contraceptive, either combined or progestogen alone [[Hatcher, 2007a](#)]
- Injectable progestogen [[Hatcher, 2007a](#)]
- Contraceptive vaginal ring [[Hatcher, 2007a](#)]
- Percutaneous contraceptive patches [[Hatcher, 2007a](#)]
- Male partner sterilization with documentation of azoospermia prior to the female subject's entry into the study, and this male is the sole partner for that subject [[Hatcher, 2007a](#)].
- Male condom plus partner use of one of the contraceptive options below:
  - Contraceptive subdermal implant
  - Intrauterine device or intrauterine system
  - Oral Contraceptive, either combined or progestogen alone [[Hatcher, 2007a](#)] Injectable progestogen [[Hatcher, 2007a](#)]
  - Contraceptive vaginal ring [[Hatcher, 2007a](#)]
  - Percutaneous contraceptive patches [[Hatcher, 2007a](#)]

If using hormonal contraceptives, including oral, injections and patches, a secondary method of contraception must be used.

This is an all inclusive list of those methods that meet the GSK definition of highly effective: having a failure rate of less than 1% per year when used consistently and, correctly and, when applicable, in accordance with the product label. For non-product methods (e.g. male sterility), the investigator determines what is consistent and correct use. The GSK definition is based on the definition provided by the ICH [[ICH, M3 \(R2\) 2009](#)].

The investigator is responsible for ensuring that subjects understand how to properly use these methods of contraception.

### 12.2.2. Collection of Pregnancy Information

- Investigator will collect pregnancy information on any female subject or female partner of male study subject who becomes pregnant while participating in or while partner is participating in this study.
- Information will be recorded on the appropriate form and submitted to GSK within 2 weeks of learning of a subject's pregnancy.
- Subject will be followed to determine the outcome of the pregnancy. The investigator will collect follow up information on mother and infant, which will be forwarded to GSK. Generally, follow-up will not be required for longer than 6 to 8 weeks beyond the estimated delivery date.
- Any termination of pregnancy will be reported, regardless of fetal status (presence or absence of anomalies) or indication for procedure.
- While pregnancy itself is not considered to be an AE or SAE, any pregnancy complication or elective termination of a pregnancy will be reported as an AE or SAE.
- A spontaneous abortion is always considered to be an SAE and will be reported as such.
- Any SAE occurring as a result of a post-study pregnancy which is considered reasonably related to the study treatment by the investigator, will be reported to GSK as described in [Appendix 4](#). While the investigator is not obligated to actively seek this information in former study participants, he or she may learn of an SAE through spontaneous reporting.

**Any female subject who becomes pregnant while participating in this study will discontinue study drug. There is no requirement to be withdrawn from the study.**

### 12.3. Appendix 3: Liver Safety Required Actions and Follow up Assessments

**Phase III-IV liver chemistry stopping and increased monitoring criteria** have been designed to assure subject safety and evaluate liver event etiology (in alignment with the FDA premarketing clinical liver safety guidance).

<http://www.fda.gov/downloads/Drugs/GuidanceComplianceRegulatoryInformation/Guidances/UCM174090.pdf>

#### Phase III-IV liver chemistry stopping criteria and required follow up assessments

Liver Chemistry Stopping Criteria - Liver Stopping Event	
ALT-absolute	ALT $\geq$ 8xULN
ALT Increase	ALT $\geq$ 5xULN but <8xULN persists for $\geq$ 2 weeks ALT $\geq$ 3xULN but <5xULN persists for $\geq$ 4 weeks
Bilirubin	ALT $\geq$ 3xULN and bilirubin $\geq$ 2xULN (>35% direct bilirubin)
INR^2	ALT $\geq$ 3xULN and INR>1.5, if INR measured
Cannot Monitor	ALT $\geq$ 5xULN but <8xULN and cannot be monitored weekly for $\geq$ 2 weeks ALT $\geq$ 3xULN but <5xULN and cannot be monitored weekly for $\geq$ 4 weeks
Symptomatic	ALT $\geq$ 3xULN associated with symptoms (new or worsening) believed to be related to liver injury or hypersensitivity
Required Actions and Follow up Assessments following ANY Liver Stopping Event	
Actions	Follow Up Assessments

 
Immediately discontinue study treatment
 
Report the event to GSK within 24 hours
 
Complete the liver event CRF and complete an SAE data collection tool if the event also meets the criteria for an SAE
 
Perform liver event follow up assessments
 
Monitor the subject until liver chemistries resolve, stabilize, or return to within baseline (see MONITORING below)
 
	
 
Viral hepatitis serology
 
Only in those with underlying chronic hepatitis B at study entry (identified by positive hepatitis B surface antigen) quantitative hepatitis B DNA and hepatitis delta antibody.
 
Blood sample for PK analysis, obtained within 24 hours after last dose
 
Serum creatine phosphokinase (CPK) and lactate dehydrogenase (LDH).
 


 
• Do not restart/rechallenge subject with study treatment unless allowed per protocol and GSK Medical Governance approval is granted
 
• If restart/rechallenge not allowed or not granted, permanently discontinue study treatment and may continue subject in the study for any protocol specified follow up assessments
 
 
MONITORING:
 
For bilirubin or INR criteria:
 
 
• Repeat liver chemistries (include ALT, AST, alkaline phosphatase, bilirubin) and perform liver event follow up assessments within 24 hrs
 
• Monitor subjects twice weekly until liver chemistries resolve, stabilize or return to within baseline
 
• A specialist or hepatology consultation is recommended
 
 
For All other criteria:
 
 
• Repeat liver chemistries (include ALT, AST, alkaline phosphatase, bilirubin) and perform liver event follow up assessments within 24-72 hrs
 
• Monitor subjects weekly until liver chemistries resolve, stabilize or return to within baseline
 
	
 
• Fractionate bilirubin, if total bilirubin <math>\geq 2 \times \text{ULN}</math>
 
• Obtain complete blood count with differential to assess eosinophilia
 
• Record the appearance or worsening of clinical symptoms of liver injury, or hypersensitivity, on the AE report form
 
• Record use of concomitant medications on the concomitant medications report form including acetaminophen, herbal remedies, other over the counter medications.
 
• Record alcohol use on the liver event alcohol intake case report form
 
 
For bilirubin or INR criteria:
 
 
• Anti-nuclear antibody, anti-smooth muscle antibody, Type 1 anti-liver kidney microsomal antibodies, and quantitative total immunoglobulin G (IgG or gamma globulins).
 
• Serum acetaminophen adduct HPLC assay (quantifies potential acetaminophen contribution to liver injury in subjects with definite or likely acetaminophen use in the preceding week [James, 2009]). NOTE: not required in China
 
• Liver imaging (ultrasound, magnetic resonance, or computerised tomography) and /or liver biopsy to evaluate liver disease: complete Liver Imaging and/or Liver Biopsy CRF forms.
 

--	--

1. Serum bilirubin fractionation should be performed if testing is available. If serum bilirubin fractionation is not immediately available, discontinue study treatment for that subject if ALT  $\geq 3 \times \text{ULN}$  and bilirubin  $\geq 2 \times \text{ULN}$ . Additionally, if serum bilirubin fractionation testing is unavailable, record presence of detectable urinary bilirubin on dipstick, indicating direct bilirubin elevations and suggesting liver injury.
2. All events of ALT  $\geq 3 \times \text{ULN}$  and bilirubin  $\geq 2 \times \text{ULN}$  (>35% direct bilirubin) or ALT  $\geq 3 \times \text{ULN}$  and INR >1.5, if INR measured which may indicate severe liver injury (possible 'Hy's Law'), **must be reported as an SAE (excluding**

- studies of hepatic impairment or cirrhosis**); INR measurement is not required and the threshold value stated will not apply to subjects receiving anticoagulants
3. New or worsening symptoms believed to be related to liver injury (such as fatigue, nausea, vomiting, right upper quadrant pain or tenderness, or jaundice) or believed to be related to hypersensitivity (such as fever, rash or eosinophilia)
  4. Includes: Hepatitis A IgM antibody; Hepatitis B surface antigen and Hepatitis B Core Antibody (IgM); Hepatitis C RNA; Cytomegalovirus IgM antibody; Epstein-Barr viral capsid antigen IgM antibody (or if unavailable, obtain heterophile antibody or monospot testing); Hepatitis E IgM antibody
  5. If hepatitis delta antibody assay cannot be performed,, it can be replaced with a PCR of hepatitis D RNA virus (where needed) [Le Gal, 2005].
  6. PK sample may not be required for subjects known to be receiving placebo or non-GSK comparator treatments. Record the date/time of the PK blood sample draw and the date/time of the last dose of study treatment prior to blood sample draw on the CRF. If the date or time of the last dose is unclear, provide the subject's best approximation. If the date/time of the last dose cannot be approximated OR a PK sample cannot be collected in the time period indicated above, do not obtain a PK sample. Instructions for sample handling and shipping are in the SPM.

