Prednisone for the unblinded (open-label) taper will be provided by the sites or by the Sponsor in certain countries in order to comply with local regulations. Use of standard release prednisone is required for the open-label taper. Prednisone doses between 60 and 20 mg will be administered during the unblinded (open label) taper. Subjects who reach 20 mg will receive the blinded prednisone from that visit. Prednisone doses below 20 mg and/or matching placebo will be provided in blister packs for blinded administration. Subjects should take their prednisone daily dose in one single daily administration in the morning.

	Study Treatment		
Product name:	Sirukumab	Placebo	Prednisone/ prednisone placebo
Dosage form:	1.0 mL Pre-filled syringe	1.0 mL Pre-filled syringe	Tablets
Unit dose strength(s)/Dosage level(s):	100 mg/mL or 50 mg/mL	--	Up to-60 mg/day
Route of Administration	SC	SC	Oral
Dosing instructions:	SC q2w (treatment arms A & B) SC q4w (treatment arm C)	SC q2w (treatment arms D & E)	20-60 mg/day open-label then 0-18 mg/day taper (blinded)

Note subjects randomized to treatment arm C will alternate between sirukumab 50 mg SC and matching placebo SC injections in order to maintain the blind (see Section 6.4).

Instructions for use of the SmartJect autoinjector will be provided to subjects and to the sites. Each step in the instructions is essential to ensure a successful delivery of study drug. It is important that the autoinjector is held against the skin at the injection site with sufficient force to disengage the safety interlock and make the push button actuatable, the actuation button is pressed to begin the injection cycle, and the autoinjector remains in place until the complete dose is delivered (second audible click or 15 seconds).

The investigator and designated site staff will be trained in the use of the SmartJect autoinjector for the SC administration of study drug. The trained site staff will be responsible for training each individual subject in the proper use of the SmartJect autoinjector. The study drug will be administered by the trained site staff during site visits until the subject is trained and confident in the use of the SmartJect auto-injector to self-administer study drug at home. If necessary a family member or carer will be trained in the use of the SmartJect autoinjector in order to administer the injection to the subject.

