Study drug will be administered by the trained site staff at the Baseline and Week 2 visits. At the Week 4 visit, subjects will self-administer study drug at the site under the supervision of the trained site staff unless they are unable or unwilling to do so. In this case, study drug will be administered by the trained site staff.

At the relevant site visits, study drug must be withheld until all patient reported outcomes (PROs) questionnaires have been completed and blood samples taken for pharmacokinetic (PK) analysis of sirukumab serum concentrations (in order to collect a pre-dose sample). The visits scheduled for PRO and PK analyses are provided in Section 7.1, Time and Events Tables.

Once these assessments are completed, subjects will self-administer study drug at the site or may have study drug administered by the trained site staff. Subjects will self-administer study drug at home in between site visits. Subjects unable or unwilling to self-administer study drug at home may be able to attend the clinic between scheduled visits for study drug administration.

Subjects who self-administer study drug at home, should be instructed to take the study drug q2w but no more than  $\pm 4$  days from the scheduled dosing day. Administrations of study drug must be at least 7 days apart. Subjects will be instructed to contact the investigator promptly in the event of any signs of an allergic reaction, infection or bleeding.

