## **6.8. Treatment of Study Treatment Overdose**

Subjects in clinical studies with sirukumab have received up to 10 mg/kg sirukumab IV q2w and no dose-limiting toxicity has been observed. No clinical information is available for sirukumab doses greater than 10 mg/kg.

For this study, any dose of sirukumab >100 mg within a 7 day period will be considered an overdose.

GSK does not recommend specific treatment for an overdose of sirukumab (see Section 5.22 on overdose in the sirukumab IB).

The investigator should refer to the approved product label for advice on an overdose of prednisone.

In the event of an overdose the investigator should:

1. Contact the Medical Monitor immediately.
2. Closely monitor the subject for AEs/serious adverse events (SAEs) and laboratory abnormalities until sirukumab can no longer be detected systemically (at least 70 days for sirukumab).
3. Obtain a plasma sample for PK analysis within 70 days from the date of the last dose of study treatment if requested by the Medical Monitor (determined on a case-by-case basis).
4. Document the quantity of the excess dose as well as the duration of the overdosing in the CRF.

Decisions regarding dose interruptions or modifications will be made by the investigator in consultation with the Medical Monitor based on the clinical evaluation of the subject.

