**Table 6 Laboratory Parameters**

Hematology		
Hemoglobin	Hematocrit	Red blood cell (RBC) count
White blood cell (WBC) count with differential	Neutrophils, absolute	Neutrophils, segs (%)
Neutrophils, bands (%)	Basophils (%)	Eosinophils (%)
Eosinophils, absolute	Lymphocytes (%)	Monocytes (%)
Platelet count		
Serum Chemistry		
Sodium	Potassium	Chloride
Bicarbonate	Blood urea nitrogen (BUN)	Creatinine
Glucose	Aspartate transaminase	Alanine transaminase
Alkaline phosphatase	Calcium	Phosphate
Albumin	Total protein	Bilirubin, direct, indirect and total
Fasting lipids		
Total cholesterol	Low density lipoprotein (LDL)	High density lipoprotein (HDL)
Triglycerides		
Serum and urine pregnancy test for premenopausal women only		
Serology for HIV, hepatitis B surface antigen, hepatitis B core antibody and hepatitis C antibody 		
Other tests		
Hemoglobin A1c	C-reactive protein (CRP) 	Erythrocyte sedimentation rate (ESR) 
QuantIFERON-TB Gold Test		

1. If hepatitis C antibody positive, a hepatitis C RNA PCR assay should be reflexively performed on a fresh sample to confirm the result
2. Investigators will remain blinded to the results of the ESR, CRP and fasting lipids after the start of treatment during Part A of the study (see Section 6.4). ESR will be analyzed at the local laboratory.
3. Required for the evaluation of efficacy.

Values for liver transaminase levels (AST, ALT), absolute neutrophil count (ANC), and platelet count that require study drug interruption and/or permanent discontinuation of study drug administration are listed below in [Table 7](#).

**Table 7 Values for Liver Transaminase Levels, Absolute Neutrophil Count, and Platelet Count That Require Study Drug Interruption and/or Permanent Discontinuation of Study Drug**

ALT or AST increased	
ALT or AST	Action
≥3xULN) for laboratory reference range.	Interrupt study drug administration, assess for symptoms, and repeat ALT/AST test as soon as possible* (see Section 5.4.3). May resume study drug when <3x ULN
Criteria for drug-induced liver injury	Permanent discontinuation of study drug
Low Absolute Neutrophil Count (ANC)	
Neutrophil count	Action
0.5 to ≤1.0 x 10  /μL (SI: 0.5 to ≤1.0 x 10  cells/L)	Interrupt study drug administration, repeat ANC test as soon as possible* May resume study drug when >1.0 x 10  /μL

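### Appendix 3 permits the dedicated liver-event PK sample only within 24 hours of the last dose and forbids it afterwards, which does not fit a drug injected every 2 or 4 weeks

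*Protocol*

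**What the plan says.** Appendix 3 (Protocol 12.3) lists the follow-up required after any liver stopping event. It includes "Blood sample for PK analysis, obtained within 24 hours after last dose". Footnote 6 rules out the sample when the dosing time is unknown, and adds that if "a PK sample cannot be collected in the time period indicated above, do not obtain a PK sample".

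The same table requires sites to "Immediately discontinue study treatment", and Section 5.4.3.1 bars restart. Its monitoring text says "Repeat liver chemistries (include ALT, AST, alkaline phosphatase, bilirubin) and perform liver event follow up assessments within" 24 hours for the bilirubin or INR criteria, and 24-72 hours for all other criteria. Two of the other criteria need ALT elevation to last at least 2 or at least 4 weeks.

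Section 6.1 gives the dosing as "SC q2w (treatment arms A & B) SC q4w (treatment arm C"). Doses between visits are self-administered at home. At clinic visits the injection is held back until "blood samples taken for pharmacokinetic (PK) analysis of sirukumab serum concentrations (in order to collect a pre-dose sample").

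Section 6.8, on overdose, treats sirukumab as detectable for at least 70 days and tells the investigator to "Obtain a plasma sample for PK analysis within 70 days from the date of the last dose of study treatment" if the Medical Monitor asks for it.

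**The concern.** Appendix 3 states that its criteria are meant to help establish the cause of a liver event, and the drug concentration around the event is part of that evidence. A 24-hour limit suits a drug taken daily. For a long-acting antibody given every 2 or 4 weeks, most events will be recognised more than a day after the injection. Because treatment stops at once and cannot restart, no later dose reopens the window. A site can meet the 24-72 hour work-up deadline and still be forbidden to draw the sample. Section 6.8 shows that the protocol regards much later samples of this drug as worth having in another setting. Appendix 3 gives no reason for excluding them here.

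**Working it through.** The plan gives no figure for the yield of this sample, so there is nothing to reproduce. The check is arithmetic on time windows.

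**Inputs from the Protocol**
- Sampling window: 24 h (Appendix 3).
- Dosing interval: 14 × 24 = 336 h for q2w; 28 × 24 = 672 h between active doses in Arm C (Section 6.1).
- Work-up time W: up to 24 h for bilirubin/INR criteria; 24-72 h for the rest (Appendix 3). The second can be read as a deadline (0-72 h) or as an interval (24-72 h). Both are shown.
- Detectability: 70 × 24 = 1,680 h (Section 6.8).

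**Assumptions, not in the documents**
- T, the time from last dose to recognition of the event, is uniform over the dosing interval, and W is uniform over its range.
- Laboratory turnaround is not stated. It is varied from 0 to 48 h.

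**Step 1. Share of the interval.** 24/336 = 7.1%; 24/672 = 3.6%. Blinded sites see an injection every 2 weeks in every arm, so in Arm C the 3.6% is the share falling within 24 h of an active dose.

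**Step 2. Chance that the sample is allowed, P(T + W ≤ 24).** For W from 0 to w, with w at least 24 h, this is (24²/2)/(interval × w) = 288/(interval × w).

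| Work-up | q2w (336 h) | q4w active (672 h) |
|---|---|---|
| Immediate | 24/336 = 7.1% | 24/672 = 3.6% |
| 0-24 h (bilirubin/INR) | 288/8,064 = 3.6% | 288/16,128 = 1.8% |
| 0-72 h (other criteria) | 288/24,192 = 1.2% | 288/48,384 = 0.6% |
| 24-72 h (other criteria) | 0% | 0% |

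**Step 3. Dose given at the detecting visit, just after the blood draw.** T then equals the turnaround L. The chance is (24 − L)/24 for bilirubin/INR events and (24 − L)/72 for other events with a 0-72 h work-up.

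| L | Bilirubin/INR | Other, 0-72 h |
|---|---|---|
| 0 h | 100% | 33% |
| 6 h | 75% | 25% |
| 12 h | 50% | 17% |
| 18 h | 25% | 8% |
| 24 h or more | 0% | 0% |

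With a 24-72 h work-up, the other criteria stay at 0% even in this case.

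**Step 4. Persistence criteria.** Table 7 (Section 7.5.6) says of ALT or AST at or above 3×ULN: "Interrupt study drug administration, assess for symptoms, and repeat ALT/AST test as soon as possible". If dosing is interrupted, the last dose is weeks old when a 2- or 4-week criterion is met, and the 24-hour window has closed. Appendix 3's increased-monitoring table instead lets treatment continue for ALT from 3 to below 8×ULN under stated conditions. These passages conflict and must be reconciled.

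**Step 5. What scheduled PK still provides.** In Part A (Table 2), chemistry is drawn at 14 post-baseline visits and PK at 10 of them (weeks 2, 4, 8, 12, 16, 20, 24, 28, 44 and 52): 10/14 = 71%. Weeks 32, 36, 40 and 48 have chemistry without PK. In Part B Table 4, PK accompanies 3 of 10 post-baseline chemistry visits (weeks 12, 52 and 104), so 7 lack it. No PK is specified for the weekly liver-monitoring visits.

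**Step 6. Reach of a 70-day window.** A full interval plus a 72 h work-up is 336 + 72 = 408 h, or 672 + 72 = 744 h. Both are below 1,680 h. Adding 4 weeks of persistence to the longer case gives 672 + 672 + 72 = 1,416 h (59 days), still inside the window if the event is recognised when the 4 weeks are complete.

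**The case against.** The best defence is that footnote 6 restricts one supplementary sample. In most of Part A a pre-dose level is taken at the same visit as the abnormal chemistry. Stopping the drug does not require leaving the study, so later scheduled PK remains possible: week 36 is followed by PK at week 44 (56 days), week 40 at week 44 (28 days) and week 48 at week 52 (28 days). Only week 32 waits longer (84 days), and PK was drawn at week 28. This stands, and it limits the loss. It does not cover weekly liver monitoring or most Part B visits.

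Four stronger readings are tempting, and the documents do not support them.

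- A reader might infer that liver events have no drug level at all. Step 5 shows otherwise.
- A reader might infer that the sample is impossible for every event. For bilirubin/INR events, which include the possible Hy's Law cases, the work-up is due within 24 hours. A valid sample is unlikely but possible, mainly when the dose was given at the detecting visit and results return quickly.
- A reader might infer that Section 6.8 contradicts Appendix 3. It is an overdose rule, applied case by case on request. A detectability period and a sampling window can coexist. Section 6.8 shows only that later samples can be informative.
- A reader might blame this rule for a *Liver PK* listing (SAP 9.6.1) without concentrations. SAP Section 2 says PK samples will not be analysed because the study was terminated, so that gap would exist under any window.

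Footnote 6 also counts from the last dose of study treatment, which Section 6.1 allows to include daily prednisone. Read that way the window would seldom close, but it would be tied to the wrong drug, since the assay in Section 7.6 measures sirukumab. That is a further reason to reword it.

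**Conclusion.** The point holds for the dedicated, event-triggered sample. Followed as written, Appendix 3 forbids most of these samples: under uniform timing on q2w dosing they are allowed in about 3.6% of bilirubin/INR events and 0-1.2% of other events. If the dose was given at the detecting visit, the figure for bilirubin/INR events runs from 100% down to 0% as turnaround goes from 0 to 24 hours or more. The wording of the rule and the interval shares (7.1% and 3.6%) come straight from the protocol. The probabilities rest on assumed uniform timing and an unstated turnaround, so they indicate scale only. The practical loss is greatest at Part A weeks 32, 36, 40 and 48, at weekly liver-monitoring visits and in Part B. Termination removes any effect on reported concentrations in this study but does not make the rule suitable. It is worth correcting because the rule works against the appendix's own aim and the correction is cheap.

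**What to change.** In Appendix 3, state that the PK sample is drawn at the liver-event work-up, and record the date and time of both the sample and the last subcutaneous sirukumab or placebo injection. Use that injection as the reference point in footnote 6 in place of study treatment. Limit the instruction not to sample to times beyond 70 days after that injection, the protocol's own detectability figure in Section 6.8, or to another window that the sponsor justifies from sirukumab PK. Separately, reconcile Table 7 with the increased-monitoring table in Appendix 3. This review takes no position on which dosing rule should stand.

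The cost is appendix wording and one extra serum tube at a visit that already takes blood. Later samples would have to be interpreted by time since injection, which the recorded times allow.
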